12.7.2. Laboratory Values – Haematology, Chemistry and Liver

Haematology				
Laboratory Parameter	Units	Category	Clinical Concern Range	
			Low Flag (< x)	High Flag (>x)
Hematocrit	Ratio of 1	Male		0.54
		Δ from BL	↓0.075	
Hemoglobin	g/L	Male		180
		Δ from BL	↓25	
Lymphocytes	x10 ⁹ / L		0.8	
Neutrophil Count	x10 ⁹ / L		1.5	
Platelet Count	x10 ⁹ / L		100	550
White Blood Cell Count (WBC)	x10 ⁹ / L		3	20

Clinical Chemistry				
Laboratory Parameter	Units	Category	Clinical Concern Range	
			Low Flag (< x)	High Flag (>x)
Albumin	g/L		30	
Calcium	mmol/L		2	2.75
Creatinine	umol/L			>1.3*ULN
Creatinine		Δ from BL		↑ 44.2
Glucose	mmol/L		3	9
Potassium	mmol/L		3	5.5
Sodium	mmol/L		130	150

Liver Function				
Test Analyte	Units	Category	Clinical Concern Range	
ALT/SGPT	U/L	High	≥ 2x ULN	
AST/SGOT	U/L	High	≥ 2x ULN	
AlkPhos	U/L	High	≥ 2x ULN	
T Bilirubin	μmol/L	High	≥ 1.5x ULN	
T. Bilirubin + ALT	μmol/L U/L	High	1.5x ULN T. Bilirubin + ≥ 2x ULN ALT	

CONFIDENTIAL

208564

12.7.3. ECG

ECG Parameter	Units	Clinical Concern Range	
		Lower	Upper
Absolute			
Absolute QTc Interval	msec		> 450
Absolute PR Interval	msec	< 110	> 220
Absolute QRS Interval	msec	< 75	> 110
Change from Baseline			
Increase from Baseline QTc	msec		> 60

12.7.4. Vital Signs

Vital Sign Parameter (Absolute)	Units	Clinical Concern Range	
		Lower	Upper
Systolic Blood Pressure	mmHg	< 85	> 160
Diastolic Blood Pressure	mmHg	< 45	> 100
Heart Rate	bpm	< 40	> 110

Vital Sign Parameter (Change from Baseline)	Units	Clinical Concern Range			
		Decrease		Increase	
		Lower	Upper	Lower	Upper
Systolic Blood Pressure	mmHg	≥ 20	≥ 40	≥ 20	≥ 40
Diastolic Blood Pressure	mmHg	≥ 10	≥ 20	≥ 10	≥ 20
Heart Rate	bpm	≥ 15	≥ 30	≥ 15	≥ 30

CONFIDENTIAL

208564

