9.4.2. Primary Endpoint(s)

Analysis	Details
Endpoints	
 • Number of participants reporting AEs and SAEs • Number of participants with vital signs (blood pressure, heart rate, body temperature) reaching a threshold of potential clinical importance • Number of participants with treatment emergent abnormal ECG findings. • Number of participants with CTCAE grade 1 or higher safety laboratory results (clinical chemistry, haematology values where CTCAE grading applies). • Number of participants with treatment emergent abnormal urinalysis findings.
Analysis	
 • For count data, the number and percentage of participants will be presented. • In addition, where continuous data is available, descriptive statistics (i.e. n, arithmetic mean, standard deviation, minimum, median, and maximum) of both raw and change from baseline data will be also presented. • CTCAE criteria (version 5) will be used to categorise laboratory safety data.

 • Statistical Analysis (Modelled) 	
 • No statistical modelling is planned.

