2. SUMMARY OF KEY PROTOCOL INFORMATION

2.1. Changes to the Protocol Defined Statistical Analysis Plan

There was an unplanned interim analysis conducted due to safety related temporary study hold criterion being met and was not specified in the protocol.

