2.2. Study Objective(s) and Endpoint(s)

Objectives	Endpoints
Primary Objectives	Primary Endpoints

 To evaluate the safety and tolerability of a single SC dose of GSK2330811 in healthy Japanese participants 	
 Number of participants reporting AEs. Number of participants reporting SAEs. Number of participants with vital signs (blood pressure, heart rate, body temperature) reaching a threshold of potential clinical importance Number of participants with treatment emergent abnormal ECG findings. Number of participants with CTCAE grade 1 or higher safety laboratory results (clinical chemistry, haematology values where CTCAE grading applies). Number of participants with treatment emergent abnormal urinalysis findings
Secondary Objectives	Secondary Endpoints

 To evaluate the pharmacokinetic (PK) profile of a single SC dose of GSK2330811 in healthy Japanese participants To assess the potential for anti-drug antibody formation following a single SC dose of GSK2330811 in healthy Japanese participants To assess effects of GSK2330811 on platelets and haemoglobin in healthy Japanese participants 	
 Pharmacokinetic parameters (Cmax, AUC, CL/F, Tmax, t_{1/2}, V_{ss}/F) Number of participants with anti-GSK2330811 antibodies Platelet nadir Time to platelet nadir Haemoglobin nadir Time to haemoglobin nadir
Exploratory Objectives	Exploratory Endpoints

 To explore the PD and the PK/PD relationship for GSK2330811 in the blood of healthy Japanese participants 	
 Serum levels of free OSM Serum levels of total OSM Levels of Thrombopoietin (TPO) Levels of Erythropoietin (EPO)

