7.3. Other Safety Analyses

The analyses of non-laboratory safety test results including ECGs and vital signs will be based on GSK Core Data Standards, unless otherwise specified.

A separate listing to capture the COVID-19 infection assessment of participants based on new eCRF page will be provided.

The details of the planned displays are presented in [Appendix 9: List of Data Displays](#).

CONFIDENTIAL

208564

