3.16.	Safety	SAFE_T4	Summary of Worst Case Urinalysis Results Post-Baseline Relative to Baseline	Tests to include: Urine blood, Urine Glucose (dipstick), Urine Ketones (dipstick), Urine Microscopy – Bacteria, Urine Microscopy - Red Blood Cells, Urine Microscopy - White Blood Cells, Urine Protein (dipstick), Urine Specific Gravity	SAC
ECG					
3.17.	Safety	EG1	Summary of ECG Findings		SAC
3.18.	Safety	EG2	Summary of ECG Values	Footnote: Average used for triplicate ECG measurements	SAC
3.19.	Safety	EG2	Summary of Change from Baseline in ECG Values	Footnote: Average used for triplicate ECG measurements	SAC
Vital Signs					
3.20.	Safety	VS1	Summary of Change from Baseline in Vital Signs		SAC
3.21.	Safety	VS7	Summary of Worst Case Vital Signs Results Relative to Potential Clinical Importance (PCI) Criteria Post-Baseline Relative to Baseline		SAC

CONFIDENTIAL

208564

Safety: Tables					
No.	Population	IDSL / Example Shell	Title	Programming Notes	Deliverable [Priority]
3.22.	Safety	SAFE_T5	Summary of Worst Case Vital Sign Results Relative to Change from Baseline Potential Clinical Importance (PCI) Criteria		SAC
Immunogenicity					
3.23.	Safety	IMM1	Occurrence of Anti-Drug Antibodies	Add footnote: Note: The denominator for confirmed positive is the total number of subjects at that visit who have immunogenicity data available.	SAC

CONFIDENTIAL

208564

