	Increase to 5-10	1 (<1%)		4 (2%)	
	Increase to 10-15	1 (<1%)		0	
	Increase to 15-20	2 (<1%)		1 (<1%)	

CONFIDENTIAL

208564

	Increase to 20-25	2 (<1%)	0
	Increase to 25-50	4 (2%)	1 (<1%)
W	n	230	232
	No Change/Decreased	222 (97%)	223 (96%)
	Any Increase	8 (3%)	9 (4%)
	Increase to NORMAL	6 (3%)	5 (2%)
	Increase to HIGH	6 (3%)	5 (2%)

Note: Little n does not include Not done or No results.

CONFIDENTIAL

208564

Example: SAFE_T5

Protocol: 208564

Population: Safety

Page 1 of n

Table 3.22
 Summary of Worst Case Vital Sign Results Relative to Change from Baseline Potential Clinical Importance (PCI) Criteria

Test (Unit)	Change Category	Placebo (N=XX)	GSK2330811 450 mg (N=XX)
Diastolic blood pressure (mmHg)	n	xx	xx
	Decrease >= 10	xx (xx%)	xx (xx%)
	Decrease >= 20	xx (xx%)	xx (xx%)
	Increase >= 10	xx (xx%)	xx (xx%)
	Increase >= 20	xx (xx%)	xx (xx%)
Heart Rate (bmp)	n	xx	xx
	Decrease >= 15	xx (xx%)	xx (xx%)
	Decrease >= 30	xx (xx%)	xx (xx%)
	Increase >= 15	xx (xx%)	xx (xx%)
	Increase >= 30	xx (xx%)	xx (xx%)
Systolic blood pressure (mmHg)	n	xx	xx
	Decrease >= 20	xx (xx%)	xx (xx%)
	Decrease >= 40	xx (xx%)	xx (xx%)
	Increase >= 20	xx (xx%)	xx (xx%)
	Increase >= 40	xx (xx%)	xx (xx%)

[figure not shown]
CONFIDENTIAL

208564

Example: SAFE_F1
 Protocol: 208564
 Population: Safety

Page 1 of n

Figure XX.XX
 Participant Profiles for Haematology by Treatment Group

Programming notes:

One legend including all participants.

Make plot as large as possible to fill space.

add (P) to denote placebo participants.

y-axis will be displayed on the left-hand side plot and the labels for the reference lines will be included on the right-hand side plot.

[figure not shown]
CONFIDENTIAL

208564

Example: SAFE_F2
 Protocol: 208564
 Population: Safety

Page 1 of n

Figure XX.XX
 Mean Profile for Haematology by Treatment Group

Programming notes:

See output 3.9 from 201247.

Make plot as large as possible to fill space.

Use different marker symbol, line pattern and colour by treatment group.

Table: Include N after treatment group and use same colour as in the plot.

[figure not shown]
CONFIDENTIAL

208564

Example: SAFE_F3
 Protocol: 208564
 Population: Safety

Page 1 of n

Figure XX.XX
 LTF Patient Profiles

Note: M = Male, F = Female, ALT = Alanine Amino Transferase, AST = Aspartate Amino Transferase, Alk. Phos. = Alkaline Phosphatase, Total Bili. = Total Bilirubin
 Clinical Concern Levels: ALT, AST and Alk. Phos: 2 times respective ULN, Total Bili: 1.5 times the ULN

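### Body temperature is a named part of the primary vital-signs count, but the SAP states no temperature limit and does not declare the component dropped

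*SAP*

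**What the plan says.** Protocol sections 1.1, 3 and 9.4.2 and SAP 2.2 give the same primary vital-signs endpoint: "Number of participants with vital signs (blood pressure, heart rate, body temperature) reaching a threshold of potential clinical importance". Protocol 8.2.2 says temperature is measured by the tympanic route, and the schedule of activities lists it with the other vital signs.

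SAP 4.5 names Appendix 7 as the place for values of potential clinical importance (PCI). Its vital-signs section, 12.7.4, has two tables. The one headed "Vital Sign Parameter (Absolute" gives lower and upper limits for systolic pressure, diastolic pressure and heart rate. The other gives change-from-baseline limits for the same three parameters.

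Appendix 9 of the SAP lists four vital-signs displays:

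- Table 3.20, "Summary of Change from Baseline in Vital Signs"
- Table 3.21, "Summary of Worst Case Vital Signs Results Relative to Potential Clinical Importance (PCI) Criteria Post-Baseline Relative to Baseline"
- Table 3.22, "Summary of Worst Case Vital Sign Results Relative to Change from Baseline Potential Clinical Importance (PCI) Criteria"
- Listing 26, which prints all vital signs for participants with any PCI value

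SAP 7.3 adds a general reference: "The analyses of non-laboratory safety test results including ECGs and vital signs will be based on GSK Core Data Standards, unless otherwise specified". SAP 2.1 records one departure from the protocol: "There was an unplanned interim analysis conducted due to safety related temporary study hold criterion being met and was not specified in the protocol".

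**The concern.** The endpoint is a count of participants who cross a threshold, and no modelling or testing is planned. For such an endpoint the threshold is the analysis. Without one for temperature, the report could give the primary vital-signs result for pressure and heart rate alone and not say that temperature was left out.

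Temperature is relevant in this study. Protocol 2.3.1 lists infection as a potential risk, and part of its mitigation is regular review of signs.

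Timing also matters. The study is sponsor-open, and SAP 2.5 reports an unplanned unblinded review of exposure data. Nothing suggests that anyone has seen temperature by arm. A limit written down before the randomisation codes are released would remove any question of its having been chosen with treatment known.

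**Working it through.** The plan gives no figure to reproduce here, so the check sets the relevant text side by side.

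**Limits in SAP 12.7.4 for each measured parameter**

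| Endpoint component | Measured parameter | Absolute limits | Change-from-baseline limits |
|---|---|---|---|
| Blood pressure | Systolic (mmHg) | < 85, > 160 | 20, 40 |
| Blood pressure | Diastolic (mmHg) | < 45, > 100 | 10, 20 |
| Heart rate | Heart rate (bpm) | < 40, > 110 | 15, 30 |
| Body temperature | Temperature | none stated | none stated |

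Components with a stated limit: 2 of 3. Measured parameters with a stated limit: 3 of 4.

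**Could the limit be elsewhere?** The SAP names body temperature three times: once in the endpoint (2.2) and twice in the schedule (12.1.1). None of these carries a limit, and the protocol gives none either.

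**Could a row have been lost in the PDF text?** Section 12.7.4 carries no redaction or missing-figure mark. The separate mock shell for Table 3.22 (SAFE_T5, SAP 12.10) shows the same three parameters, so a lost row is unlikely.

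**Was the component dropped on purpose?** SAP 2.1 lists one change, the unplanned interim analysis, and SAP 2.2 still includes temperature. The SAP is therefore at odds with itself as well as with the protocol.

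**Effect on the displays.** Three of the four depend on PCI limits.

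- Table 3.21: under the stated limits, temperature is not counted.
- Table 3.22: no temperature row in the shell. A row is needed only if a change limit is set, since an absolute limit alone would satisfy the endpoint.
- Listing 26: a participant whose only excursion is in temperature is not selected. A participant flagged on pressure or heart rate has all vital signs printed, temperature included.
- Table 3.20: needs no limit, but summarises change and counts nobody.

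**Observed values.** Protocol 9.4.2 plans "descriptive statistics (i.e. n, arithmetic mean, standard deviation, minimum, median, and maximum) of both raw and change from baseline data". ECG has one table for values (3.18) and one for change (3.19), whereas no vital-signs table is titled for observed values. Standard shell VS1, used for Table 3.20, may include them, but its content is not in the documents. This bears only on what would remain for temperature if it became descriptive.

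**The case against.** The strongest objection is that the sponsor's standards may already settle the matter. SAP 7.3 bases vital-signs analyses on them, Tables 3.20 and 3.21 and Listing 26 use standard shells, and 12.7.4 does not say its list is exhaustive. This stands as a limit on certainty: the documents show that no limit is stated, not that temperature will certainly go uncounted. It does not close the gap. SAP 7.3 gives way where something else is specified, 12.7.4 does specify vital-signs limits, and a programmer could fairly take that list as complete. If a default exists, citing it resolves the point.

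Second, nothing shows a decision to drop temperature, so SAP 2.1 may have had nothing to declare. An omitted row is at least as likely as an undisclosed change, and no concealment is implied. Section 2.1 matters because it rules out a declared removal as the explanation.

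Third, the study is small and descriptive, and an abnormal vital sign judged clinically significant is an adverse event under Protocol 10.3.1. That coverage is real but partial. It rests on the investigator's judgement, whereas the endpoint counts against a fixed threshold and is separate from the adverse-event count. The infection argument is also indirect, because the protocol speaks of signs without naming temperature.

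Finally, the likely visible result is an absent row, which a careful reader could notice, and not a false zero.

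**Conclusion.** The point holds. The SAP keeps body temperature in a primary endpoint and gives no rule for counting it. The gap covers 1 of the 3 named components, in both arms, for about 10 planned participants and at most 14. Of the four planned vital-signs displays, three rely on PCI limits, and the two that bear directly on the count are Table 3.21 and Listing 26. The number of participants who would go uncounted cannot be estimated from the documents.

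Confidence is high that no limit is stated in the text available. The practical consequence assumes that the limits in 12.7.4 are applied as written and that no sponsor default fills the gap. No hypothesis test is affected and the study is not invalidated. This is a clear, easily corrected gap in a primary-endpoint definition, and it should be corrected.

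**What to change.** Before the unblinding criteria in SAP 2.6 (step 3) are met, and without looking at temperature by arm, reconcile SAP 2.2 with SAP 12.7.4 in one of two ways.

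- **Keep the count.** Add a body-temperature criterion to 12.7.4, taken from the sponsor's data standards or another cited source. Apply it in Table 3.21 and Listing 26, and in Table 3.22 if a change limit exists. The cost is one table row and minor programming in existing displays.
- **Make temperature descriptive.** State in SAP 2.1 that this changes the primary endpoint, and name the display that gives observed temperature values, since the protocol plans both raw and change summaries. The cost is one sentence and, if shell VS1 does not already show them, observed temperature values in one table.

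Neither route needs new data. This review proposes no value for the limit.

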12.8. Appendix 8: Abbreviations & Trademarks

12.8.1. Abbreviations

Abbreviation	Description
AE	Adverse Event
AUC	Area Under the Curve
A&R	Analysis and Reporting
CI	Confidence Interval
CL/F	Apparent Clearance
CPMS	Clinical Pharmacology Modelling & Simulation
CS	Clinical Statistics
CSR	Clinical Study Report
DBF	Database Freeze
DBR	Database Release
DOB	Date of Birth
DP	Decimal Places
eCRF	Electronic Case Record Form
EMA	European Medicines Agency
FDA	Food and Drug Administration
FDAAA	Food and Drug Administration Clinical Results Disclosure Requirements
GSK	GlaxoSmithKline
IA	Interim Analysis
ICH	International Conference on Harmonization
IDSL	Integrated Data Standards Library
IP	Investigational Product
LLN	Lower Limit of Normal
NCA	Non-Compartmental Analysis
PCI	Potential Clinical Importance
PD	Pharmacodynamic
PDMP	Protocol Deviation Management Plan
PK	Pharmacokinetic
QC	Quality Control
QTcF	Frederica's QT Interval Corrected for Heart Rate
QTcB	Bazett's QT Interval Corrected for Heart Rate
RAP	Reporting & Analysis Plan
SAC	Statistical Analysis Complete
SOP	Standard Operation Procedure
TA	Therapeutic Area
TFL	Tables, Figures & Listings
t _{last}	Time of last quantifiable concentration
T _{max}	Time of occurrence of C _{max}
t _{1/2}	Half-life
ULN	Upper Limit of Normal
V _{ss/F}	Steady state apparent volume of distribution
%AUC _{ex}	Percentage of AUC(0-inf) obtained by extrapolation

CONFIDENTIAL

208564

12.8.2. Trademarks

Trademarks of the GlaxoSmithKline Group of Companies	Trademarks not owned by the GlaxoSmithKline Group of Companies
None	SAS WinNonlin

CONFIDENTIAL

208564

12.9. Appendix 9: List of Data Displays

12.9.1. Data Display Numbering

The following numbering will be applied for RAP generated displays:

Section	Tables	Figures
Study Population	1.1 to 1.11	
Safety	3.1 to 3.23	3.1 to 3.5
Pharmacokinetic	4.1 to 4.3	4.1 to 4.3
Pharmacodynamic and / or Biomarker	6.1 to 6.6	6.1 to 6.3
Pharmacokinetic / Pharmacodynamic		7.1
Section	Listings	
ICH Listings	1 to 27	
Other Listings	28 to 35	

12.9.2. Mock Example Shell Referencing

Non IDSL specifications will be referenced as indicated and if required example mock-up displays provided in [Appendix 10: Example Mock Shells for Data Displays](#).

Section	Figure	Table	Listing
Study Population	POP_Fn	POP_Tn	POP_Ln
Safety	SAFE_Fn	SAFE_Tn	SAFE_Ln
Pharmacokinetic	PK_Fn	PK_Tn	PK_Ln
Pharmacodynamic and / or Biomarker	PD_Fn	PD_Tn	PD_Ln
Pharmacokinetic / Pharmacodynamic	PKPD_Fn	PKPD_Tn	PK/PD_Ln

NOTES:

- Non-Standard displays are indicated in the 'IDSL / Example Shell' or 'Programming Notes' column as '[Non-Standard] + Reference.'

12.9.3. Deliverables

Delivery ^[1]	Description
SAC	Final Statistical Analysis Complete

NOTES:

- Indicates priority (i.e. order) in which displays will be generated for the reporting effort

CONFIDENTIAL

208564

12.9.4. Study Population Tables

Study Population Tables					
No.	Population	IDSL / Example Shell	Title	Programming Notes	Deliverable [Priority]
Subject Disposition					
1.1.	Safety	ES1	Summary of Subject Disposition	Include total column	SAC
1.2.	Screened	ES6	Summary of Screening Status and Reasons for Screen Failure		SAC
Protocol Deviation					
1.3.	Safety	DV1	Summary of Important Protocol Deviations Not Related to COVID-19		SAC
1.4.	Safety	DV1	Summary of Important Protocol Deviations Related to COVID-19		
Population Analysed					
1.5.	Screened	SP1	Summary of Study Populations		SAC
Demography					
1.6.	Safety	DM1	Summary of Demographic Characteristics	Include: Height, Weight, and BMI	SAC
1.7.	Enrolled	DM11	Summary of Age Ranges		SAC
1.8.	Safety	DM6	Summary of Race and Racial Combinations		SAC
Concomitant Medications and other Medical Conditions					
1.9.	Safety	MH4	Summary of Past Medical Conditions		SAC
1.10.	Safety	MH4	Summary of Current Medical Conditions		SAC
1.11.	Safety	CM8	Summary of Concomitant Medications		SAC

CONFIDENTIAL

208564

12.9.5. Safety Tables

Safety: Tables					
No.	Population	IDSL / Example Shell	Title	Programming Notes	Deliverable [Priority]
Adverse Events (AEs)					
3.1.	Safety	AE1	Summary of All Adverse Events by System Organ Class and Preferred Term		SAC
3.2.	Safety	AE5A	Summary of Adverse Events by System Organ Class and Preferred Term and Maximum Intensity		SAC
3.3.	Safety	AE1	Summary of Drug-Related Adverse Events by System Organ Class and Preferred Term		SAC
3.4.	Safety	AE15	Summary of Non-serious Adverse Events by System Organ Class and Preferred Term (Number of Subjects and Occurrences)		SAC
Serious and Other Significant Adverse Events					
3.5.	Safety	AE16	Summary of Serious Adverse Events by System Organ Class and Preferred Term (Number of Subjects and Occurrences)		SAC
3.6.	Safety	AE3	Summary of Serious Drug-Related Adverse Events by Overall Frequency		SAC
3.7.	Safety	AE1	Summary of Adverse Events Leading to Permanent Discontinuation of Study Treatment or Withdrawal from Study by System Organ Class and Preferred Term		SAC
Chemistry					
3.8.	Safety	LB1	Summary of Chemistry		SAC
3.9.	Safety	LB17	Summary of Worst-Case Chemistry Results Relative to Potential Clinical Importance (PCI) Criteria Post-Baseline Relative to Baseline		SAC

CONFIDENTIAL

208564

Safety: Tables					
No.	Population	IDSL / Example Shell	Title	Programming Notes	Deliverable [Priority]
3.10.	Safety	SAFE_T1	Summary of Chemistry Results by Maximum CTCAE Grade	Footnote: "CTCAE criteria, V5.0: November 27, 2017"	SAC
Haematology					
3.11.	Safety	LB1	Summary of Haematology	By parameter	SAC
3.12.	Safety	LB16	Summary of Haematology Results by Maximum CTCAE Grade Increase Post-Baseline Relative to Baseline	Footnote: "CTCAE criteria, V5.0: November 27, 2017"	SAC
3.13.	Safety	LB17	Summary of Worst Case Haematology Results Relative to Potential Clinical Importance (PCI) Criteria Post-Baseline Relative to Baseline		SAC
3.14.	Safety	SAFE_T2	Summary of Nadirs for Selected Haematology Parameters	By parameter, treatment group Produce for Platelet count and Haemoglobin. Footnote: "Nadir is the lowest post-baseline value of the parameter"	SAC
3.15.	Safety	SAFE_T3	Summary of Days to Nadir of Selected Haematology Parameters	by parameter, treatment group. Produce for Platelet count and Haemoglobin. Footnote: "Nadir is the lowest post-baseline value of the parameter"	SAC

CONFIDENTIAL

208564

Safety: Tables					
No.	Population	IDSL / Example Shell	Title	Programming Notes	Deliverable [Priority]
Urinalysis					
3.16.	Safety	SAFE_T4	Summary of Worst Case Urinalysis Results Post-Baseline Relative to Baseline	Tests to include: Urine blood, Urine Glucose (dipstick), Urine Ketones (dipstick), Urine Microscopy – Bacteria, Urine Microscopy - Red Blood Cells, Urine Microscopy - White Blood Cells, Urine Protein (dipstick), Urine Specific Gravity	SAC
ECG					
3.17.	Safety	EG1	Summary of ECG Findings		SAC
3.18.	Safety	EG2	Summary of ECG Values	Footnote: Average used for triplicate ECG measurements	SAC
3.19.	Safety	EG2	Summary of Change from Baseline in ECG Values	Footnote: Average used for triplicate ECG measurements	SAC
Vital Signs					
3.20.	Safety	VS1	Summary of Change from Baseline in Vital Signs		SAC
3.21.	Safety	VS7	Summary of Worst Case Vital Signs Results Relative to Potential Clinical Importance (PCI) Criteria Post-Baseline Relative to Baseline		SAC

CONFIDENTIAL

208564

Safety: Tables					
No.	Population	IDSL / Example Shell	Title	Programming Notes	Deliverable [Priority]
3.22.	Safety	SAFE_T5	Summary of Worst Case Vital Sign Results Relative to Change from Baseline Potential Clinical Importance (PCI) Criteria		SAC
Immunogenicity					
3.23.	Safety	IMM1	Occurrence of Anti-Drug Antibodies	Add footnote: Note: The denominator for confirmed positive is the total number of subjects at that visit who have immunogenicity data available.	SAC

CONFIDENTIAL

208564

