5.1. Inclusion Criteria

Participants are eligible to be included in the study only if all of the following criteria apply:

Age

1. Participants must be 18 to 65 years of age inclusive, at the time of signing the informed consent.

Type of Participant and Disease Characteristics

2. Participants who are overtly healthy as determined by medical evaluation including medical history, physical examination, laboratory tests and 12-lead ECGs
3. A participant with a clinical abnormality or laboratory parameter(s) outside the reference range for the healthy population being studied that is not specifically listed in the inclusion or exclusion criteria may be included if the investigator and GSK Medical Monitor agree and document that the finding is unlikely to introduce additional risk factors and will not interfere with the study procedures or interpretation.

Weight

4. Body weight ≥ 45 kg and body mass index (BMI) within the range 18.5-29.9 kg/m² (inclusive).

Sex

5. Male

Informed Consent

6. Capable of giving signed informed consent which includes compliance with the requirements and restrictions listed in the ICF and in this protocol.

Geographical Ancestry

7. Japanese ancestry, defined as having been born in Japan, being descendants of four ethnic Japanese grandparents and two ethnic Japanese parents, holding a Japanese passport or identity papers, and being able to speak Japanese. Participants should have lived outside Japan for less than 10 years at the time of screening.

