7.2. Clinical Laboratory Analyses

Laboratory evaluations including the analyses of chemistry laboratory tests, haematology laboratory tests, urinalysis, and liver function tests will be based on GSK Core Data Standards. The details of the planned displays are in [Appendix 9: List of Data Displays](#).

Descriptive statistics (n, arithmetic mean, standard deviation, median, minimum, and maximum) will be calculated for nadirs for platelet count and haemoglobin.

Descriptive statistics (n, median, minimum, maximum and range) will also be calculated for time to nadir for platelet count and haemoglobin.

Laboratory safety will be graded using CTCAE criteria version 5. CTCAE grade 1 or higher safety laboratory results will be presented (where CTCAE grading applies).

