12.10. Appendix 10: Example Mock Shells for Data Displays

Example: SAFE T1

Protocol: 208564

Population: Safety

Page 1 of n

Table XX.XX
Summary of Chemistry Results by Maximum CTCAE Grade

Test: Creatinine (UMOL/L)

Event: Creatinine increased

Treatment	N	Grade 1	Grade 2	Grade 3	Grade 4
Placebo	XX	XX	XX.X	XX.XX	XX.X
GSK2330811 450 mg	XX	XX	XX.X	XX.XX	XX.X

Note: CTCAE criteria, V5.0: November 17, 2017 graded on laboratory test value.

Only events with at least one graded value are shown.

CONFIDENTIAL

208564

Example: SAFE_T2

Protocol: 208564

Population: Safety

Page 1 of n

Table XX.XX

Summary of Nadirs for Selected Haematology Parameters [as Percent Change from Baseline]

Lab Test (unit)	Treatment	N	n	Mean	SD	Median	Min	Max
Hemoglobin (G/L)	Placebo	XX	XX	XX.X	XX.XX	XX.X	XX.X	XX.X
	GSK2330811 450 mg	XX	XX	XX.X	XX.XX	XX.X	XX.X	XX.X

.....

Note: Nadir is the lowest post-baseline value of the parameter.

CONFIDENTIAL

208564

Example: SAFE_T3

Protocol: 208564

Population: Safety

Page 1 of n

Table XX.XX
Summary of Days to Nadir for Selected Haematology Parameters

Lab Test (unit)	Treatment	N	n	Median	Min	Max	Range
Hemoglobin (G/L)	Placebo	XX	XX	XX	XX	XX	XX
	GSK2330811 450 mg	XX	XX	XX	XX	XX	XX

.....

Note: Nadir is the lowest post-baseline value of the parameter.

CONFIDENTIAL

208564

Example: SAFE_T4

Programming note: please flag to study team/ statistics when summarizing if observe any character variables not the minimum value and not presented as an increase category.

Tests to summarise as X=BACTM_URQ (minimum value=NONE SEEN)

Tests to summarise as Y= BLD_URC, PROT_URG, KETO_URG, GLUC_URG (minimum value=NEGATIVE)

Tests to summarise as Z= RBCM_URG, WBCM_URG (minimum value=NONE SEEN)

Tests to summarise as W= SG_URG (minimum value=Low)

Example modified from UR1

Protocol: ABC123456

Page 1 of 1

Population: Safety/Other study specific

Table X
Summary of Worst Case Urinalysis Results Post-Baseline Relative to Baseline

Test	n	Treatment A (N=248)		Treatment B (N=247)	
X		230		232	
	No Change/Decreased	222 (97%)		223 (96%)	
	Any Increase	8 (3%)		9 (4%)	
	Increase to MANY	6 (3%)		5 (2%)	
Y	n	230		232	
	No Change/Decreased	222 (96%)		222 (96%)	
	Any Increase	7 (3%)		10 (4%)	
	Increase to TRACE	2 (<1%)		5 (2%)	
	Increase to 1+	1 (<1%)		4 (2%)	
	Increase to 2+	1 (<1%)		0	
	Increase to 3+	4 (2%)		1 (<1%)	
Z	n	230		232	
	No Change/Decreased	222 (96%)		222 (96%)	
	Any Increase	7 (3%)		10 (4%)	
	Increase to 0-1	2 (<1%)		5 (2%)	

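### The two tables for the primary laboratory endpoint count differently: as titled, the haematology table omits unchanged baseline grades that the endpoint wording includes

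*SAP*

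**What the plan says.** **Endpoint.** Protocol 9.4.2 lists as one primary endpoint the "Number of participants with CTCAE grade 1 or higher safety laboratory results", covering chemistry and haematology where CTCAE grading applies. SAP 2.2 repeats it. The wording is not limited to treatment-emergent results or to grade increases. The neighbouring urinalysis endpoint is limited in that way ("Number of participants with treatment emergent abnormal urinalysis findings"), and so is the ECG endpoint. SAP 7.2 says only that "CTCAE grade 1 or higher safety laboratory results will be presented (where CTCAE grading applies") and gives no rule for grades already present at baseline.

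**Tables.** SAP 12.9.5 lists one CTCAE summary per domain:

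- Table 3.10, chemistry, shell SAFE_T1: "Summary of Chemistry Results by Maximum CTCAE Grade". The shell in SAP 12.10 is laid out by test and event, with columns for grades 1 to 4. It has no baseline column and no post-baseline condition. Its only inclusion rule is "Only events with at least one graded value are shown".
- Table 3.12, haematology, standard shell LB16: "Summary of Haematology Results by Maximum CTCAE Grade Increase Post-Baseline Relative to Baseline".

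No grade-increase table is listed for chemistry, and no maximum-grade table for haematology.

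**Entry.** Protocol 5.1 allows a participant with "laboratory parameter(s) outside the reference range for the healthy population being studied that is not specifically listed" in the entry criteria, if the investigator and medical monitor document that the finding is unlikely to add risk or to interfere with interpretation. Protocol 5.2 excludes platelets or haemoglobin below normal at screening.

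**The concern.** The endpoint is a single definition, so a reader expects the same rule in both domains. As titled, a stable grade 1 triglyceride appears in the chemistry table, while a stable grade 1 neutrophil count does not appear in the haematology table. The SAP gives no reason for the difference. The study is descriptive, with about 7 active and 3 placebo participants, so these counts are themselves the primary result and no model or test follows them. What is at stake is whether the reported haematology number is the one the protocol defines, and whether the two domains can be read side by side.

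**Working it through.** **Step 1. The two rules applied to the same participant.** Take baseline grade b and maximum post-dose grade m.

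| b to m | Any post-baseline grade 1 or higher (m ≥ 1) | Grade increase (m > b), Table 3.12 | Maximum grade if pre-dose values enter |
|---|---|---|---|
| 0 to 0 | no | no | no |
| 0 to 1 | yes | yes | yes |
| 1 to 1 | **yes** | **no** | yes |
| 1 to 2 | yes | yes | yes |
| 1 to 0 | no | no | **yes** |

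The 1-to-1 row separates the tables on either reading of Table 3.10. The 1-to-0 row depends on whether Table 3.10 takes pre-dose values. SAP 12.3.1 classifies assessments by phase but does not say which phase this table uses.

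**Step 2. Which tests can produce a 1-to-1 pattern.** From the grading table in SAP 12.7.1:

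- *Fixed-limit chemistry, affected:* cholesterol (grade 1 from the ULN), triglycerides (from 1.71 mmol/L), creatinine at grade 1, calcium, sodium, potassium and low glucose. Lipids are scheduled only at Day 1 pre-dose and Day 21 (Protocol Appendix 2), and Protocol 5.2 has no lipid exclusion.
- *Baseline-relative chemistry, not affected:* with an abnormal baseline, ALT and AST need at least 1.5 x baseline for grade 1, and bilirubin needs more than 1.0 x baseline. Grade 1 high glucose must be above baseline. An ALT of 1.4 x ULN before and after gives a ratio of 1.4/1.4 = 1.0, below 1.5, so no grade. An unchanged abnormal bilirubin also has ratio 1.0, so no grade.
- *Haematology:* low platelets or haemoglobin at screening are excluded, so baseline grade for a fall is normally 0 and the rules nearly coincide. The gap is mainly in lymphocytes, neutrophils and white cells.

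**Step 3. Size of one affected participant.** The protocol's own precision table (Section 9.2, Table 2) uses a Beta(1,1) prior, so the limits are the 2.5% and 97.5% quantiles of Beta(1 + x, 1 + n − x). Recomputed:

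- 0/7: 0.32% to 36.94% (stated 0.3% to 37%)
- 1/7: 3.19% to 52.65% (stated 3.2% to 53%)

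Both reproduce. One active participant with an unchanged grade 1 and no other event therefore reads 1/7 (14%, 3.2% to 53%) under maximum grade and 0/7 (0%, 0.3% to 37%) under grade increase. On placebo one participant is 1/3, or 33 points.

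**Step 4. How often.** The documents do not say. For illustration only, if a share p of participants carried a persisting grade in an affected test, the chance of at least one among 7 would be 1 − (1 − p)^7. That is 30%, 52%, 79% and 92% for p = 5%, 10%, 20% and 30%. For 3 placebo participants it is 14%, 27%, 49% and 66%. These values of p are assumptions, not estimates.

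**The case against.** **Table 3.10 is not the faulty table.** The endpoint carries no treatment-emergent limit while its neighbours do, so maximum grade is the closer match to the wording. This stands. A reader might infer that the chemistry counts are inflated by pre-existing abnormalities and should move to the Table 3.12 layout. The documents do not support that. It would be an objection to the protocol's definition, and the move would take chemistry away from the protocol count. Nor does any sentence say that pre-dose values enter Table 3.10; the SAP is silent.

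**A headline number is not available.** A reader might take a share of healthy men with some out-of-range chemistry value, say 10% to 40%, and multiply by 7 and 3 to get 0.7 to 2.8 and 0.3 to 1.2 spurious events. No cell of the SAFE_T1 shell reports such a pooled count. Urea, albumin, total protein, alkaline phosphatase, HDL and LDL are measured but have no row in the CTCAE table. The baseline-relative tests drop out, and the abnormality would also have to persist if only post-baseline values count.

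**Other displays help.** Tables 3.9 and 3.13 treat the domains alike, Listing 20 gives graded values for both, and with about 10 participants (at most 14) each case can be checked by hand. This lowers the stakes, and a claim that baseline imbalance would pass as a drug signal goes too far. It does not close the gap. Tables 3.9 and 3.13 use potential-clinical-importance limits, which for neutrophils (1.5), lymphocytes (0.8) and white cells (3) start below the grade 1 range and which omit cholesterol and triglycerides. Listing 20 gives no count.

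**LB16 is not in the documents.** This also stands: the content of Table 3.12 is read from its title, and the standard shell might show more.

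**Conclusion.** The point holds as an inconsistency of display in a primary endpoint, of minor severity. Table 3.12, as titled, does not give the grade 1 or higher count that Protocol 9.4.2 defines, because unchanged baseline grades fall out. Table 3.10 is closer to the definition but leaves the treatment of pre-dose values open. The effect is confined to the fixed-limit chemistry tests and, mainly, to lymphocytes, neutrophils and white cells. The study's main haematological risks, falls in platelets and haemoglobin, are hardly touched. The 14-point and 33-point steps assume the planned 7 and 3 participants. The conclusion rests on the table titles and the SAFE_T1 shell. No sample-size or error-rate figure changes.

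**What to change.** Use one rule for both domains and state it in SAP 7.2. In Tables 3.10 and 3.12 report, by treatment group:

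1. the number of participants with any post-baseline grade 1 or higher result, stating that pre-dose values are excluded; this is the protocol count;
2. beside it, the number with a grade increase from baseline.

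The endpoint wording does not itself mention pre-dose values, so the exclusion should be written down. Because SAFE_T1 is laid out test by test, the first number needs its own row across tests. Moving chemistry to the Table 3.12 layout alone would not be enough, since neither table would then give the protocol count.

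The cost is one extra row or column per table, from data already collected and shells already planned. Design, sample size and data collection are unchanged.
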